## 4.3 Efficacy Analyses

The ITT population will be the primary population for all efficacy analyses. The PP population will be used for supportive analyses. In efficacy analyses, subjects will be analyzed according to the treatment to which they were randomized.

The primary and BMD-related secondary efficacy endpoints will be derived from the Bioclinicacorrected BMD measurements.

BMD scans may be deemed unevaluable at the first reading and a repeat BMD scan may be performed. The re-scan BMD assessment will be recorded as an unscheduled visit for the corresponding nominal visit. To determine the assessment that will be used for a given study visit by the analysis window convention, all BMD assessments (including unscheduled BMD assessments) will be considered. In the efficacy analyses by nominal visit, unscheduled BMD assessments will be used if the BMD assessment at the nominal visit is not available but an unscheduled BMD assessment for the same nominal visit is available.

Analyses of the BMD-related efficacy endpoints and the serum markers of bone metabolism (s-PINP and s-CTX) will be conducted using the analysis visit windows defined in Table 4 of Section 3.12 as the primary analysis. Analyses of the BMD-related efficacy endpoints and the serum markers of bone metabolism (s-PINP and s-CTX) using the nominal visits will also be presented as supportive analyses.

All confidence intervals, statistical tests, and p-values will be reported as nominal 2-sided. The primary and key secondary efficacy endpoints will be assessed at the significance level of 0.01. All other efficacy endpoints will be assessed at a significance level of 0.05.

## 4.3.1 Primary Efficacy Endpoint

The primary efficacy endpoint is the percent change from baseline in lumbar spine BMD at 12 months. The mean of percent changes from baseline in lumbar spine BMD to 12 months will be estimated for each treatment group, and the abaloparatide-SC will be compared to placebo using

difference in group means. The primary comparison of abaloparatide-SC with placebo will be based on the ITT population.

The missing data from this study will be reviewed carefully to evaluate any missing data patterns. As this study is not designed to systematically collect data from subjects who discontinue treatment early, the "retrieved dropouts" approach for handling missing data is not applicable to this study. To appropriately address the possibility of data missing not at random, the primary analysis will be based on a pattern mixture model (PMM) analysis with multiple imputation using the wash-out imputation method. This method uses sequential regression and wash-out imputation methodology to impute missing values after a subject's discontinuation from the study. The missing primary endpoint values for subjects in the abaloparatide-SC group will be imputed with observed baseline and data (including imputed values) from the placebo group; no intermediate values from the abaloparatide-SC group will be used in the imputation for the abaloparatide-SC group. For subjects in the placebo group, intermediate observed values from the completers in the placebo group will be used while imputing missing values during the 12-month treatment period. The PROC MI methodology for imputation of monotone missing data patterns will be used to impute the outcome variables at consecutive visits in a sequential (chain) manner. Each of these imputed datasets will be analyzed using analysis of covariance (ANCOVA) model with treatment and DXA instrument manufacturer as fixed effects, and the baseline lumbar spine BMD as a covariate. Results from all imputed datasets will be combined using PROC MIANALYZE for overall statistical inference. The statistical test will be 2-sided comparing abaloparatide-SC to placebo; Both 99% and 95% confidence intervals (CIs) will be presented together with the estimated p-values. The detailed imputation and analysis steps are described below:

- 1. Intermittent missing data in the placebo treatment group will be imputed using MCMC methods, assuming MAR. SAS PROC MI will be utilized for this step using the MCMC impute=monotone option. A total of 100 datasets will be created. These datasets will be utilized in Step #2.
- 2. The remaining missing values in the placebo group with a monotone missing data pattern will be imputed in this step. Missing data will be imputed assuming data are MAR. Only data (both observed and imputed) from subjects in the placebo group will be utilized in this step. SAS PROC MI will be used to impute missing values utilizing the monotone reg option. This will be performed for the 100 datasets. After this step, the 100 datasets will be fully imputed for the placebo treatment group.
- 3. The missing values at Month 12 in the abaloparatide-SC group will be imputed in this step. Control-based PMM imputation will be performed. With this imputation model, the missing values in the abaloparatide-SC group will not be constructed from the observed data in the abaloparatide-SC group but rather from the observed baseline and data (including imputed values) from the placebo group at Month 12. The MNAR statement in SAS PROC MI will be used to impute missing values. This will be performed for the 100 datasets.
- 4. A total of 100 fully imputed datasets will be created for both treatment groups. Since multiple imputation is a stochastic method, slight differences in output can be expected for different initial states of the random number generator. The seed numbers will be identified in the SAS programs to allow for reproducibility.

- 5. After the missing data imputation is completed using the above steps, percentage change values will be calculated in each of the imputed datasets at each visit.
- 6. These 100 datasets will be analyzed using ANCOVA models with fixed effect of treatment group and DXA instrument manufacturer, and baseline lumbar spine BMD as a covariate for the primary efficacy endpoint.
- 7. Treatment effects (difference in LS means between treatments) from these 100 analyses will then be combined using Rubin's Method via SAS PROC MIANALYZE procedure for the primary endpoint.

As a sensitivity analysis, the primary efficacy endpoint will also be analyzed using a Mixed Model for Repeated Measures (MMRM) analysis. The MMRM model will include the fixed effects of treatment, DXA instrument manufacturer, visit, and treatment-by-visit interaction, with the baseline lumbar spine BMD as covariate. Imputation for missing data is not necessary for the MMRM analysis because the model uses a restricted maximum likelihood (REML) based on the repeated-measures approach. For the MMRM model, an unstructured variance-covariance matrix shared between the two treatment groups will be used to model the within-subject errors over the visits. The Kenward-Roger approximation will be used to estimate denominator degrees of freedom and to adjust standard errors (Kenward, 1997). Analyses will be implemented using the SAS PROC MIXED procedure. The treatment comparison will be obtained by testing the contrast (difference in least squares mean) between the two treatment groups at Month 12 (Visit 8). The statistical test will be 2-sided comparing abaloparatide-SC to placebo; 99% CIs will be presented together with the estimated p-values.

As supportive analysis, the primary efficacy endpoint will also be analyzed using an ANCOVA model using the last observation carried forward (LOCF) method. The ANCOVA model will include treatment and DXA instrument manufacturer as fixed effects, and the baseline lumbar spine BMD as covariate. To test for statistically significant differences between the treatment groups, the treatment comparison will be derived by testing the contrast (difference in least squares mean) between the two treatment groups at the Month 12 (Visit 8) visit. Missing data imputation based on the LOCF method will be performed as follows:

- If baseline BMD is missing, no imputation for post-baseline value will be done and this subject's data will be excluded from the analysis.
- If baseline BMD is observed, missing post-baseline BMD will be imputed by the last observed value prior to the missing assessment. That is, if a value is missing at a post-baseline time point, the post-baseline BMD will be imputed using the last value observed at any time (could be a value obtained at an unscheduled visit) between baseline (inclusive) and the specified post-baseline time point.

The primary analysis using the PMM with the wash-out imputation method, and the other analyses using the MMRM model and the ANCOVA model using LOCF method, will be repeated using the PP population to support the findings from the ITT population.

For the primary efficacy endpoint using PMM analysis with wash-out imputation, subgroup analyses for each of the subgroups defined in Section 3.8 will be performed. The treatment groups will be compared within each subgroup. A forest plot of the estimated least square (LS) mean differences between the treatment groups (and corresponding 99% CIs) will be presented

by subgroup. Additional exploratory analyses examining subgroup effect and treatment by subgroup interaction may be performed, if warranted.

The efficacy analysis using MMRM model will also be repeated for the Antibody population, in which the subjects who are ADA+ at any post-baseline time point will be compared with subjects who are ADA- at all post-baseline time points. The MMRM model will include the fixed effects of ADA status, DXA instrument manufacturer, visit, and ADA status-by-visit interaction, with the baseline lumbar spine BMD as covariate.

To investigate the effect of the COVID-19 pandemic, the following sensitivity analyses will also be performed:

- a) PMM analysis with wash-out imputation for subjects who completed or withdrew from the study before 01 March 2020 and for subjects who completed or withdrew from the study on or after 01 March 2020. The analysis visit windows described in Table 4 will be used.
- b) PMM analysis with wash-out imputation using the nominal visit.
- c) PMM analysis with wash-out imputation excluding BMD measurements collected outside the allowable time period for data collection. In this analysis, BMD assessments are allocated to a Visit based on the inclusion rules shown in Table 5 below re: Sensitivity Analysis c).
- d) PMM analysis with wash-out imputation excluding BMD measurements which are more than 30 days after the ideal visit day. In this analysis, BMD assessments are allocated to a Visit based on the inclusion rules shown in Table 5 below re: Sensitivity Analysis d).

Visit	Ideal Visit Day	Sensitivity Analysis c): Allowable days from first dose of study drug	Sensitivity Analysis d): Allowable days from first dose of study drug
Month 3	90	2 —120 days	2—120 days
Month 6	180	121—270 days	121—210 days
Month 12	360	271—390 days	271—390 days

 Table 5:
 Visit Windows for DXA Assessments for Sensitivity Analyses.

It is possible that more than 1 assessment for a parameter may be obtained within the same visit window. In such circumstances, the assessment with the date closest to the ideal visit day will be used. In the event that 2 assessments are equidistant to the ideal visit day, the later of the assessments will be used.

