6.2.1. Schedule of Assessments and Procedures

A comprehensive Schedule of Assessments and Procedures is presented in Table 3.

Due to the ongoing COVID-19 pandemic, arrangements may also be made, contingent on the subject's consent and in compliance with country, state, and local requirements, to have a study visit conducted at the subject's home by site staff. If this occurs, blood and/or urine samples may be collected at the subject's home and then sent to the central laboratory for processing and analysis. Study drug may also be delivered to the subject's home, if needed, to enable the subject to continue administering their study drug daily.

Table 3:Schedule of Assessments and Procedures

	Visit	1	2	3	4	5	6	7	8	9
Procedure	Study Day/Month:	Screening	Pretreatmen t	Day 1	Month 1	Month 3	Month 6	Month 9	Month 12/ Early Termination	Month 13 Follow- up
Visit Window (1	Days)	N/A ¹	± 4	± 4	± 4	± 4	± 4	± 4	± 4	± 7
Informed consent		Х								
Verification of e	entry criteria	X	Х							
Physical examin	nation ²	X								
Review of medi	cal history ³	X								
Symptom-directed physical examination			Х	Х	X	Х	Х	Х	Х	Х
Vital signs ⁴		X	Х	Х	Х	X	Х	Х	Х	Х
Weight measurement		X		Х	Х		Х		Х	
Height measurement ⁵		Х	Х	Х	Х	Х	Х	Х	Х	Х
Electrocardiogram ⁶		X		Х					Х	Х
Urinalysis (dipstick) ⁷		X			Х		Х		Х	
Chemistry blood collection		X			Х		Х		Х	
Hematology blood collection		X			Х		Х		Х	
Coagulation (PT and PTT) blood		X							Х	
PTH (1–84)		X							X	
25-hydroxyvitamin D level		X							X	
1,25-dihydroxy vitamin D level		X							Х	
Total testosterone and SHBG		X							Х	
Estradiol		X								
Thyroid stimulating hormone ⁸		X								
PK samples (see Table 4)							Х	X	X	
Study medication assignment via IRT				Х						
Injection training for subjects			Х							

Table 3:Schedule of Assessments and Procedure	s (Continued)
---	---------------

	Visit	1	2	3	4	5	6	7	8	9
Procedure	Study Day/Month:	Screening	Pretreatment	Day 1	Month 1	Month 3	Month 6	Month 9	Month 12/ Early Termination	Month 13 Follow-up
Visit Window (Days	s)	N/A ¹	± 4	± 4	± 4	± 4	± 4	± 4	± 4	± 7
Calcium and vitami	n D supplements		Daily administration							
Study medication ad	dministration		Daily administration							
Serum markers of b (s-PINP and s-CTX	one metabolism			Х	Х	Х	Х		X	
Serum calcium and	albumin ⁹			Х	Х	Х	Х	X		
24-hour urine collection (for calcium:creatinine and creatinine clearance) ¹⁰				Х		Х				
Radiologic (lumbar and thoracic vertebrae) assessments		X								

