6.6.1. Dual Energy X-ray Absorptiometry

All subjects will have areal bone density (aBMD) measurements taken via DXA of the lumbar spine, total hip, femoral neck, at Screening (Visit 1), wrist at Day 1 (Visit 3); spine, total hip, femoral neck, and wrist at Month 3 (Visit 5), Month 6 (Visit 7), and Month 12 (Visit 8). Lumbar spine scans must include L1 through L4. Hip scans will include the entire proximal femur to about 2 cm below the lesser trochanter. DXA bone density assessments will be performed at the forearm to measure BMD of the distal one-third radius and ultra-distal radius. For hip and wrist scans, the same side should be used for all scans at all visits. If a subject fractures a hip or forearm being examined during the study, no further scans of either hip or forearm will be acquired.

For screening purposes, DXA scans of the lumbar spine, total hip, and femoral neck taken up to 35 days prior to the beginning of the Screening Period may be used to determine study eligibility. DXA scans should be performed using a study-approved scanner (and read by the study central DXA reader) up to 35 days prior to the subject's Screening Visit.

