6.7. Discontinuation from the Study

Subjects may voluntarily discontinue from the study for any reason at any time.

Any subject who demonstrates decreases in $BMD \ge 7\%$ from baseline of this study at the lumbar spine or total hip will have the assessment repeated and, if confirmed, will be notified by the Investigator, and be withdrawn from the study. Subjects sustaining a radiologically confirmed incident vertebral or nonvertebral fragility fracture will be informed of the finding and will be counseled as to treatment options and may discontinue or choose to remain on the study. Those subjects who sustain an incident fracture during the study and elect to remain in the study will be asked to sign an additional informed consent document advising them of an increased risk for subsequent fracture.

Subjects who decide they do not wish to participate in the study further should return for the assessments indicated for the Month 12/Early Termination and 30 days later for the Month 13/Follow-up Visit in the Schedule of Assessments and Procedures (Table 3). If they fail

to return for these assessments for unknown reasons, every effort (e.g., telephone, email, and letter) should be made to contact them.

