8.4.2. Analysis of the Primary Efficacy Endpoint(s)

The primary efficacy endpoint will be the percent change in lumbar spine BMD from baseline to 12 months. The analyses will be based on the ITT Population.

The missing data from this study will be reviewed carefully to evaluate any missing data patterns. As this study was not designed to systematically collect data from subjects who discontinue treatment early, the "retrieved dropouts" approach for handling missing data is not applicable for this study. To appropriately address the possibility of data missing not at random, the primary analysis will be based on a pattern-mixture model (PMM) analysis with multiple

imputation using the wash-out imputation method. This method uses sequential regression and wash-out imputation methodology to impute missing values after a subject's discontinuation from the study. The missing primary endpoint values for subjects in the abaloparatide-SC group will be imputed with the observed baseline and data from the placebo group; no intermediate values from the abaloparatide-SC group will be used in the imputation for the abaloparatide-SC group. For subjects in the placebo group, intermediate observed values from the completers in the placebo group will be used while imputing missing values during the 12-month Treatment Period. The PROC MI methodology for imputation of monotone missing data patterns will be used to impute the outcome variables at consecutive visits in a sequential (chain) manner. Each of these imputed datasets will be analyzed using analysis of covariance (ANCOVA) with treatment and DXA instrument manufacturer as fixed effects and the baseline lumbar spine BMD as a covariate. Results from all imputed datasets will be combined using PROC MIANALYZE for overall statistical inference. The statistical tests will be 2-sided comparing abaloparatide-SC to placebo; 99% CIs will be presented together with the estimated p-values.

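### The scope sentence limits wash-out to values missing after discontinuation, but SAP step 3 washes out every missing active-arm Month 12 value, and COVID-19 sensitivity analyses c and d extend this to observed late scans

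*SAP*

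**What the plan says.** Protocol 8.4.2 and SAP 4.3.1 both describe the primary analysis as using "wash-out imputation methodology to impute missing values after a subject's discontinuation from the study". In each document the next sentence drops that condition. The protocol has "The missing primary endpoint values for subjects in the abaloparatide-SC group will be imputed with the observed baseline and data from the placebo group"; the SAP has "The missing primary endpoint values for subjects in the abaloparatide-SC group will be imputed with observed baseline and data", with placebo imputed values included. Both then bar intermediate active-arm values from the active-arm imputation.

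The SAP goes on to numbered steps. Step 1: "Intermittent missing data in the placebo treatment group will be imputed using MCMC methods, assuming MAR". Step 2 completes the placebo arm by monotone regression under MAR. Step 3: "The missing values at Month 12 in the abaloparatide-SC group will be imputed in this step. Control-based PMM imputation will be performed". No MAR step is given for the active arm.

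The documents foresee missing scans without discontinuation:

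- SAP 4.3 allows for scans read as unevaluable, with a repeat scan optional.
- The COVID-19 log in SAP 4.1 lists assessments not done, missing data and missed visits separately from discontinuation. Protocol 6.2.1 adds "Study drug may also be delivered to the subject's home, if needed, to enable the subject to continue administering their study drug daily".
- For hip sites only, Protocol 6.6.1 states "If a subject fractures a hip or forearm being examined during the study, no further scans of either hip or forearm will be acquired", while under Protocol 6.7 a man with a confirmed fragility fracture is "counseled as to treatment options and may discontinue or choose to remain on the study".

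On timing, SAP Table 4 takes any scan from day 271 as Month 12, with no upper limit. Table 5 cuts Month 12 to days 271-390 in both sensitivity analyses c and d, which then apply wash-out. SAP 5 records that the FDA recommended the wash-out method.

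**The concern.** Both documents introduce wash-out after noting that data are not collected systematically once a man stops treatment early. A man still injecting daily who lacks one usable scan is not in that position. He is nevertheless imputed as placebo, while a placebo man with an intermittent gap gets an MAR step. The reported estimate would then be diluted by missed scans as well as by discontinuation, and the text gives two descriptions of which values are washed out.

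Analyses c and d are meant to show whether late scans matter. If a late scan is removed and a placebo-based value put in its place, any movement in the Month 12 estimate mixes scan timing with lost treatment effect.

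**Working it through.** **1. The plan's own power figures.** Inputs (SAP 3.1): 150 and 75 men; 2-sided alpha 0.01; effect and SD 6.5 and 6.0 (spine), 2.2 and 3.5 (total hip), 2.0 and 4.1 (femoral neck); drop-out 10%. Power = Φ(effect/SE − 2.576), with SE = SD × √(1/150 + 1/75) = SD × 0.1414.

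- Total hip: 2.2/0.495 = 4.445, power 96.9% (stated 96%).
- Femoral neck: 2.0/0.580 = 3.449, power 80.9% (stated 80%).
- Lumbar spine: above 99.9% (stated at least 99%).

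With 10% removed (135 and 67.5 men), total hip is 95.0% and femoral neck 75.7%. The stated 80% is met only without drop-out.

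**2. What the text does to each active-arm man at Month 12.**

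| Man | Scope sentence | Step 3 | Analyses c and d |
|---|---|---|---|
| Discontinued, no scan from day 271 | wash-out | wash-out | wash-out |
| Stayed, no usable scan from day 271 | not covered | wash-out | wash-out |
| Stayed, only scan from day 271 falls after day 390 | observed | observed | scan discarded, then wash-out |

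The scope sentence and step 3 differ in the second row. In the third row the loss occurs only in c and d.

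**3. Dilution.** Let d be the share of the active arm that discontinues and m the share missing Month 12 without discontinuing. Assume that washed-out men carry no effect and the others carry the full effect. As written, the expected difference is effect × (1 − d − m). With wash-out limited to discontinuers and within-arm MAR for the rest, it is effect × (1 − d). The gap is m × effect: per 1% of the active arm (1.5 of 150 men), 0.065, 0.022 and 0.020 points. With d = 10% and an assumed m = 5%:

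| Site | As written | Restricted | Gap |
|---|---|---|---|
| Lumbar spine | 5.525 | 5.85 | 0.325 |
| Total hip | 1.87 | 1.98 | 0.11 |
| Femoral neck | 1.70 | 1.80 | 0.10 |

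**4. Power, by simulation.** The main simulation ran 4,000 trials per scenario with 100 imputations, Rubin's rules and ANCOVA on treatment and baseline (DXA manufacturer omitted). Assumed: three sets of visit correlations (Month 6 with Month 12 of 0.4, 0.6 or 0.8); baseline correlation −0.1; active means at Months 3 and 6 equal to 50% and 75% of the Month 12 effect. The 10% drop-out was read two ways: m added to it, or m included in it. Loss in power points, as written against restricted:

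| Assumed m | Total hip | Femoral neck |
|---|---|---|
| 1% | 0.4-0.8 | 1.2-1.6 |
| 2% | 1.1-1.5 | 2.4-3.4 |
| 5% | 2.2-4.2 | 5.7-8.5 |

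Lumbar-spine power was 1.000 under both rules at m = 5%. A separate, simpler simulation (3,000 trials, no covariates or intermediate visits, m added to 10% drop-out) gave 86% against 89% at total hip and 57% against 64% at femoral neck for m = 5%. With m = 0, wash-out of the planned 10% alone gave about 90% and 65%.

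**5. Type I error.** Under the null (femoral neck, 20,000 trials, m = 5%), rejection was 0.0029 and 0.0044 as written, and 0.0047 and 0.0069 with restricted wash-out, for the two drop-out readings. All are below 0.01.

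**6. Analyses c and d.** Even if scan timing has no effect, the Month 12 estimate falls by 0.065, 0.022 and 0.020 points per 1% of active-arm men whose only scan from day 271 is after day 390. Their Month 12 windows are identical; they differ only at Month 6 (121-270 against 121-210 days). Step 3 ignores active-arm Month 6 values, so at Month 12 they can differ only through placebo men's Month 6 scans.

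**The case against.** A reader might infer that the protocol and SAP disagree, or that the choice is left to programming. Neither holds. The two documents carry nearly the same text, the tension lies inside each, and step 3 is specific enough to settle the programming on the broad reading.

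Washing out every missing active value is a coherent, cautious way to allow for data missing not at random. Calling it biased presupposes an estimand that the documents do not state, and the FDA advice is not available here. This stands: changing the primary rule must depend on that advice.

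MAR is also weak where a hip fracture caused the gap, because the event bears on efficacy. And the COVID-19 log has a category for missed or modified drug, so not having discontinued does not prove full treatment. Both points stand, and the fracture example cannot touch the spine endpoint.

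The share m is probably small: the Month 12 window has no upper limit, make-up scans are allowed, re-scans count, and inability to complete procedures is a withdrawal reason (Protocol 4.3.1). At m = 1% the dilution is 0.065/0.894 = 0.07 SE at the spine and 0.03 to 0.04 SE at the hip sites (SE for 135 and 67.5 men).

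Analysis d is not redundant. It tightens the Month 6 window, and SAP 4.3.2 carries the sensitivity analyses to Month 6 BMD.

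Finally, step 3 and the MMRM roughly bracket the answer. But MMRM and LOCF treat discontinuers and stayers alike, so no planned analysis estimates wash-out after discontinuation only.

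**Conclusion.** The concern holds in limited form, with severity between minor and should. The scope sentence in Protocol 8.4.2 and SAP 4.3.1 does not describe what step 3 does, and men who stayed in the study without a usable Month 12 scan are imputed as placebo. The cost is a diluted estimate and some power at the second and third steps of the fixed sequence. A stronger reading, that the primary conclusion is at risk or that type I error is inflated, is not supported: the dilution favours the null and lumbar-spine power is untouched.

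The size rests on m, which the documents do not give; 5% is illustrative. The power losses also rest on the assumed correlations and mean profile.

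The defect in c and d is firmer, because it does not depend on which scope the FDA advice intended. For the primary endpoint they are nearly the same check, and neither isolates scan timing. They lie outside the fixed sequence, so no loss of power is claimed there.

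**What to change.** 1. In c and d, impute active-arm values excluded by the window rule in men who did not discontinue under MAR within the active arm, from their own visits. Keep wash-out for values missing after discontinuation.
2. Reconcile the scope sentence in Protocol 8.4.2 and SAP 4.3.1 with step 3, checking the intended scope against the FDA advice cited in SAP 5 before unblinding.
   - If the advice meant discontinuation only, restrict step 3, use within-arm MAR for the other gaps (MCMC for intermittent ones, then monotone regression for Month 12), and keep the all-missing version as a sensitivity analysis.
   - If it meant all missing values, keep step 3 as primary, correct the sentence, and add the discontinuation-only version as a sensitivity analysis.
3. Do not assume plain MAR for hip values missing because of a hip fracture. Keep wash-out for those few men, or show both.
4. State that the same rule applies to Month 3 and 6 BMD and to s-PINP and s-CTX, since step 3 names Month 12 only.

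Cost: a discontinuation flag by man and visit (disposition and COVID-19 log data are already collected), two within-arm imputation steps and a few lines of SAP text. If the primary scope is narrowed, the primary estimate becomes slightly less conservative. The change to c and d leaves the primary analysis as it is.
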